depressed patients with increased inflammation may have unique responsiveness to drugs that target DA. Indeed, preclinical and clinical studies demonstrate that chronic administration of inflammatory stimuli leads to decreased DA availability in ventral striatum (VS) in association with decreased VS activation to rewarding stimuli. In addition, higher inflammation as reflected by CRP is directly linked to lower FC between the DA-rich VS and the ventromedial prefrontal cortex (vmPFC) in MD patients using resting state fMRI. These inflammation-related decreases in VS-vmPFC FC in depressed patients in turn were associated with motivational deficits consistent with an impact of inflammation on RDoC positive valence constructs. Our preliminary data also indicate that administration of the DA-ergic drug L-DOPA increases VS-vmPFC FC (and effort-based motivation) in MD patients with high (CRP>2mg/L) but not low (CRP≤2mg/L) inflammation, using a longitudinal pre- post- neuroimaging design. These data suggest that this circuit and the related behaviors may be especially responsive to DA'ergic medications. Thus, the relationship between CRP and resting state FC within classic reward circuitry in MD patients provides a unique opportunity whereby a functional target in the brain can be used to establish whether there exists differential responsiveness to currently available antidepressants that can be revealed by an inflammatory biomarker (CRP) that is regularly used in clinical practice. Accordingly, this proposal will employ a match/mismatch design, wherein patients with MD and increased inflammation (CRP>2mg/L) and anhedonia will be randomized to bupropion (match) or escitalopram (mismatch). A cut-off of CRP>2mg/L will be used because it predicted increased FC in response to L-DOPA and serves as an excellent translational proxy for a composite of inflammatory mediators in periphery and brain. CRP>2mg/L has also been used in the cardiovascular literature as a threshold for treatment of inflammation. Increased anhedonia will be defined as a score of 2 or greater on item 1 of the PHQ-9.. To examine FC in rewardrelated circuitry, fMRI will be conducted at baseline and after 4 and 8 weeks of treatment. We hypothesize that bupropion (vs escitalopram) will increase FC within reward circuitry in association with improved objective and clinical measures of motivation in patients with high inflammation and anhedonia at baseline. To test this hypothesis, these aims are proposed:

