Baseline and Study Procedures: After screening, subjects will undergo fMRI and behavioral assessments at baseline followed by stratification by sex and double-blind randomization to either bupropion XL 150mg/d or escitalopram 10mg/d as indicated in Table 1. The randomization scheme will be implemented by research pharmacy, and all patients and study staff will be blinded to treatment assignment. Patients will be randomized in blocks of 4. After 2 weeks, subjects with a HDRS-17_>7_will be increased to bupropion XL 300mg/d or escitalopram 20mg/d as tolerated. fMRI scanning and behavioral assessments will be repeated at 4 and 8 weeks. Vital signs, safety labs, urine toxicology and adverse events will be collected as indicated in Table 1. The primary outcome (Aim 1) will be targeted VS-vmPFC FC as detailed below. Secondary outcomes (Aim 2) will include RDoC positive valence constructs including objective assessments of effort-based decision making and clinician-administered and self-report assessments of motivation/anhedonia (see below). Additional (exploratory) outcomes will include treatment response over time and adverse events.

Table 1. Schedule of Study Procedures and Assessments

	Virtual	Visit 1 Screen	Visit 2		Visit 3	Visit 4	Visit 5	Virtual	Visit 6
Assessments	Intake		Screen B	Base- line A	Base- line B		Wk 4	Wk 6	Wk 8
Consent	Х								
PHQ-9, Medical / Psychiatric Screening***	Х	[X]	[X]						
FERN MRI Screening Form***	[X]	х					Х		Х
ATRQ, Medical History, SCID V-modified (Mood, Anxiety, PTSD modules), Bipolarity index	X								
Laboratory Eval*, Urinalysis, height weight***		Х							
Rapid CRP (Finger Stick)***		Х	Х						
Physical Exam			Х						
Vital Signs		Х	Х		Х	Х	Х		Х
Adverse events**, Concomitant Meds***	Х	Х	Х		Х	Х	Х	х	Х
Urine toxicology screen, pregnancy test***		Х		 	Х		Х		Х
Research bloods†				Х			Х		Х
Neurocognitive Battery				Х		Х	Х		Х
EEfRT (computer-based)				Х	Х	Х	Х		Х
Demographics, habits, CTQ				Х					
MAP, IDS-SR, STAI, BAI, PCL-5, PSS				Х		Х	Х	Х	Х
fMRI					Х		Х		Х
SHAPS-C, CSSRS, CGI					х	Х	Х	Х	Х
HAM-A [Baseline only]****, HAM-D-17					Х	Х	Х		Х
Randomization to bupropion / escitalopram					х				

PI: [name] Sponsor: NIMH

Medication dispensing /compliance check§			Х	Х	Х	Х	Х
Adjustment of medication#				Х	Х	Х	
Discharge/discharge planning					Х	Х	Х

^{*} Laboratory evaluation will include the comprehensive metabolic panel, thyroid-stimulating hormone (TSH), CBC with diff, and plasma CRP.

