
Targeted FC will serve as the primary outcome and will be calculated as the degree of correlation in activity between a 3mm3 radius sphere in VS (see Fig. 1A)^{25, 62} and the vmPFC cluster identified as being reward-sensitive in neuroimaging meta-analyses⁶³ and as used to define vmPFC in our previous work (MNI coordinates x=0, y=44, z=-8, cluster size=1408 mm3 and encompassing parts of BA11 and ventral BA32 of ACC). 25, 62, 64 This method will ensure rigor and reproducibility and application of results to potential future trials because the seeds and ROI cluster are predefined as opposed to those derived from whole-brain and data-driven analyses which are determined based on the specific patient sample. Zscores will be extracted and the change in mean FC values compared to baseline will be calculated. FC between bilateral VS seeds and the vmPFC ROI will be examined separately and treatment-driven change in FC in either the right or left VS will be considered in the analysis. However, based on our previous work in MD and IFN-alpha-induced depression ^{13, 25} and preliminary studies above, we anticipate that changes in FC will be more pronounced on the left side. Additional Analyses for Publication and Dissemination: In addition to the targeted FC that will serve as the primary outcome, hypothesis-driven and data-driven whole-brain analysis will also be explored and compared before and after L-DOPA and placebo. Consistent with our previously published data,65 these analyses will include VS seed-to-voxelwise comparisons of bupropion versus escitalopram, as well as network analyses using GBC and PBNA, as a secondary outcome measure and to identify other circuits that may be differentially affected by the two treatments. For all analyses, concentration of CRP and final dose will be explored as linear predictors of response.

Assessments of Positive Valence (Motivational) Constructs

Objective: Effort-Expenditure for Rewards Task (EEfRT): The EEfRT task is a multi-trial game in which participants are given an opportunity to choose different task difficulty levels to obtain monetary rewards. The task is 20 min, and first 50 trials are analyzed. The proportion of hard-task choices across each level of probability is calculated. Lower proportions of hard task choices indicate decreased motivation.

PI: [name] Sponsor: NIMH

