Research bloods will be collected between 9-11AM by venipuncture into EDTA-containing vacutainer tubes using standard sterile technique. Plasma for the evaluation of concentrations of CRP will be obtained along with additional plasma, buffy coat and a tempus tube for future studies. Plasma and buffy coat will be removed separately, aliquoted into siliconized polypropylene tubes, and stored at -80°C until batched assay of CRP. Bloods will also be collected by venipuncture into Tempus mRNA tubes and directly placed in freezer storage at -20°C. In order to collect immune cells for future analyses, we will additionally collect 10 ml of whole blood in EDTA at room temperature for immune cell extraction. Some de-identified samples may be sent to other labs for additional analysis for future studies. *C-reactive protein (CRP):* Plasma CRP will be assessed with a high sensitivity turbidimetric assay. Sensitivity is 0.18 mg/L, range of measure is 0.2 to 80 mg/L, and functional sensitivity (at 20% CV) is 0.2 mg/L.

7. Management of MRI Incidental Findings

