Aim 1: To determine whether bupropion (vs escitalopram) will increase FC in reward circuitry. Hypothesis 1: Bupropion vs escitalopram will increase VS-vmPFC FC in depressed patients with high CRP and anhedonia at baseline. Primary Endpoint: Targeted VS-vmPFC FC at 8 weeks. Predictors: group (bupropion vs escitalopram), time (baseline, 8 weeks), and group x time interactions. Covariates: Primary: Age, sex, BMI, race. Additional covariates: Number of depressive episodes, length of current depressive episode (in months), treatment trials (ATRQ), age of onset, and family history of depression (ves/no), weeks on targeted dose of medication, Analysis Plan: Subjects will be randomized to two different treatment groups and scanned across two visits. Consequently, a factorial mixed-effects models for repeated measures (MMRM) will be employed with group, time and group x time interaction on targeted VS-vmPFC FC as fixed effects and each subject's baseline (identity) as random effects. Linear and multi-level mixed effects will be evaluated using both unstructured and autoregressive covariance structures and restricted maximum likelihood estimation and will be used to predict random effects (slope and intercept) in addition to fixed effects, optimized using Bayesian Information Criteria (BIC). Primary and additional covariates will be entered in all models as random variables after testing for significant associations. Given the inherently noisy nature of the covariates, model tuning to optimize the balance between explanatory (r²) and noise variables (root mean square error) will be undertaken to select the most parsimonious models using BIC. The MMRM will also be augmented using Elastic net generalized regression models using group||time nesting approaches. Models will be selected using model comparison metrics. All analyses will be conducted in accordance with published guidelines.⁷⁶ Exploratory analysis: A similar analysis as indicated above will be conducted on fMRI scans conducted at 4 weeks. The 4-week scan will be conducted based on the rapid effects seen with dopamine agonists in our preliminary studies with L-dopa (data not shown).

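### CRP and final dose are planned as predictors of response, but no CRP-by-treatment term is specified and final dose is set after randomisation

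*Combined protocol and SAP*

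**What the plan says.** The statement is in Section 5, in the paragraph defining targeted connectivity, under the run-in heading Additional Analyses for Publication and Dissemination. It says, of every analysis, that "concentration of CRP and final dose will be explored as linear predictors of response". It is the only sentence that puts CRP into an analysis model.

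Section 10, Aim 1 gives the model terms: "Predictors: group (bupropion vs escitalopram), time (baseline, 8 weeks), and group x time interactions". The first covariate list reads "Covariates: Primary: Age, sex, BMI, race". CRP is in neither that list nor the additional one. The additional list does include "weeks on targeted dose of medication". Aims 2 and 3 take their covariates from Aim 1.

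Section 4 gives the purpose. The circuit is said to offer a functional target that "can be used to establish whether there exists differential responsiveness to currently available antidepressants that can be revealed by an inflammatory biomarker (CRP").

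Final dose is described in two places. Section 5 (Baseline and Study Procedures) says that patients scoring above 7 on the HDRS-17 after two weeks "will be increased to bupropion XL 300mg/d or escitalopram 20mg/d as tolerated". The footnote to Table 1 on medication adjustment instead allows a move to two pills at Week 2 or Week 4, depending on tolerability, and mentions no symptom score.

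**The concern.** There are two separate problems.

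**CRP.** Asking whether CRP predicts response is different from asking whether CRP predicts a larger bupropion-escitalopram difference. Only the second bears on choosing a drug by CRP, and it needs a treatment interaction. Without one, a CRP coefficient could be read as support for biomarker-guided choice when it shows only prognosis. It could also be near zero when CRP acts in opposite directions in the two arms.

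**Final dose.** Dose is fixed after treatment starts and, under the Section 5 rule, partly by how the patient is doing at week 2. As a predictor of response it is confounded by early response. In a model that also holds group it adjusts for something treatment itself may have changed, so the group coefficient no longer estimates the full treatment effect. Weeks on the targeted dose has the same defect, and it is listed for the primary model.

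**Working it through.** **1. The plan's own figure.** Section 11 gives connectivity changes of 0.20 (SD 0.16) and 0.07 (SD 0.10), d = 0.97, and 36 patients in total. Pooled SD = sqrt((0.16² + 0.10²)/2) = 0.1334, so d = 0.13/0.1334 = 0.974. By the noncentral t (two-sided 0.05 assumed, as sidedness is not stated), power is 0.807 at 18 per arm and 0.848 at 20 per arm. The stated figure reproduces. The documents give no figure for any CRP analysis.

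**2. CRP with and without the interaction.** Simulated model: change in connectivity = 0.97 × group + arm-specific slope × CRP + error. There are 20 patients per arm, CRP is standardised and the residual SD is 1. The slopes are assumptions. The outcome is already a change score, so CRP x group here stands for CRP x group x time. The CRP-only column comes from a model with group and CRP; the interaction column comes from that model plus CRP x group.

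| Slope, escitalopram / bupropion | Mean CRP coefficient | CRP-only term significant | Interaction significant |
|---|---|---|---|
| -0.485 / +0.485 (purely differential) | about 0 | 6.6% | 79% |
| 0 / 0.97 (differential, one arm) | 0.49 | 72% | 79% |
| 0.5 / 0.5 (purely prognostic) | 0.50 | 84% | 5% |

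Rows two and three give almost the same CRP coefficient, but they have opposite implications for drug choice.

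**3. What the interaction can deliver.** The standard error of a slope difference is sqrt(1/20 + 1/20) = 0.316, on 36 df. The slope difference detectable with 80% power is 0.91 residual SD per SD of CRP (0.91/0.316 = 2.88 standard errors). Power is 0.12 for a difference of 0.25, 0.32 for 0.485 and 0.64 for 0.75. A difference of 0.485 (half the planned d) needs about 68 per arm.

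**4. Final dose as a predictor.** Dose was given no causal effect. A patient moves up when early improvement falls below a cut-off that up-titrates about 75% when there is no group effect. Early improvement correlates with connectivity change at an assumed value. The 0.43 is borrowed from the connectivity-motivation correlation in Section 11 as one point in a range. The fitted model holds group and dose step. Ranges cover true group effects of 0 and 0.97.

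| Correlation | Dose coefficient (SD) | Dose falsely significant | Group coefficient when truth is 0.97 |
|---|---|---|---|
| 0.3 | about -0.5 | 27-29% | 0.92 |
| 0.43 | about -0.7 | 50-55% | 0.86 |
| 0.6 | about -1.0 | 83-87% | 0.76 |

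Relative shrinkage of the group coefficient is 0.05/0.97 = 5%, 0.11/0.97 = 11% and 0.21/0.97 = 22%.

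**5. Collinearity, which depends on coding.** Suppose dose enters in mg (150/300 versus 10/20) alongside group, with a share p of each arm at the higher step (assumed). The mean doses are 150(1+p) and 10(1+p). The between-arm variance is (140(1+p))²/4 = 4900(1+p)². The average within-arm variance is (150² + 10²)/2 × p(1-p) = 11300p(1-p). VIF = 1 + between/within:

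- p = 0.5: 1 + 11025/2825 = 4.90, SE × 2.21
- p = 0.7: 1 + 14161/2373 = 6.97, SE × 2.64
- p = 0.9: 1 + 17689/1017 = 18.39, SE × 4.29

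If dose is coded as one or two pills with equal titration in both arms, the VIF is 1.0. With 50% versus 90% up-titrated it is 1 + (0.4²/4)/((0.25 + 0.09)/2) = 1 + 0.04/0.17 = 1.24, SE × 1.11.

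**The case against.** The sentence on CRP and dose gives no model. It does not say that CRP is pooled over arms, that it is untransformed, or that dose is in mg or shares a model with group. A reader might infer that the plan commits to a pooled, prognostic CRP test. The text supports only the narrower statement that no interaction is specified.

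A reader might also infer that a few extreme CRP values will drive the fit, since there is no upper eligibility limit and the assay's "range of measure is 0.2 to 80 mg/L". That is an instrument range, not an enrolled distribution. Screening uses physical examination and laboratory tests to rule out acute inflammation or infection, so the documents do not establish this.

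The two- to four-fold inflation of the standard error is likewise no consequence of the plan. It needs mg coding and a shared model, and the Table 1 footnote counts pills.

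The analysis is exploratory. CRP is built into the design by enrolling only patients above 2 mg/L, and the opening summary leaves biomarker-guided choice to larger trials. An interaction among 40 patients above the threshold cannot settle it.

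These points limit the claim but do not remove it. The stated purpose still has no matching term. Dose is post-randomisation under either titration description. The summary also presents this pilot as groundwork for larger trials, for which an interaction estimate with its interval is more useful than a CRP coefficient alone.

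**Conclusion.** The point holds as a minor one. The planned use of CRP does not address the differential-response question in Section 4, because no treatment interaction is specified. Using final dose to predict response is unsound whichever titration text applies.

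The false-positive rates of about 27% to 87% rest on the Section 5 symptom-based rule, about 75% up-titration, and correlations of 0.3 to 0.6. None of these correlations or shares is given in the documents as an expectation for this trial. If titration followed tolerability alone, as in the Table 1 footnote, dose would still be post-randomisation, but these figures would not carry over. Bias in the treatment estimate (5% to 22% shrinkage here) arises only if dose is fitted with group. That is not stated for final dose, but it is possible for weeks on the targeted dose, which Section 10 lists among the Aim 1 covariates.

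It would be wrong to conclude that the primary group x time comparison or its sample size is undermined, or that adding the interaction would answer the biomarker question. It would give a hypothesis-generating estimate within the high-CRP range.

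**What to change.** - In Sections 5 and 10, specify an exploratory group x time x log(baseline CRP) term, with its lower-order terms. Report it as an estimate with a confidence interval. State that it applies only above 2 mg/L and is imprecise at 40 patients.
- Name the CRP measurement used. CRP is taken at screening and from research bloods at baseline, Week 4 and Week 8, and the plan does not choose. A pre-randomisation value is needed.
- Keep final dose and weeks on the targeted dose out of any model that estimates the treatment effect. Report dose step by arm descriptively, without causal interpretation.
- Reconcile the titration text in Section 5 with the Table 1 footnote on both trigger and timing, so that the dose table can be interpreted.

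The cost is analysis wording and one reconciliation. No new patients, visits or assays are needed. The drawback is a wide interval for the interaction, which should be accepted and stated.

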Hypothesis 1: Our preliminary data from depressed (major depression – MD) patients with high inflammation (CRP >2 mg/L, n=7) administered a dopaminergic agent, L-DOPA, and placebo control was used to estimate the anticipated change in VS-vmPFC FC in response to treatment (bupropion) and control (escitalopram) conditions in the proposed study. The expected change in FC in response to bupropion and escitalopram (the withinsubject effects of these conditions) was then used to calculate the effect size (ES) and sample size per group that will be required to detect a significant difference between the response to bupropion versus escitalopram (the between-subjects effect) with alpha= 0.05 and power >0.80. Accordingly, based on the mean and standard deviation for the change in FC after L-DOPA (0.2±0.16), we can expect a large ES for the expected within-subject effects of bupropion (Cohen's $d_7 = 1.25$, which would require only 8 subjects to detect). Based

Figure 1: Estimated power for between-subject comparisons of the FC response to bupropion versus escitalopram. Sample size (x-axis) and power (y-axis) for ES (d) = 0.97. The proposed total sample size of 40 (dashed line, n=20 per group) will yeild power >0.8.

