on the mean and standard deviation for the change in FC after placebo (0.07±0.10), we expected a medium effect size for the effects of escitalopram (Cohen's d₂ = 0.7), representing ~30-40% increase in FC and consistent with a ~30% placebo effect commonly observed in trials in MD patients.⁷⁸ Based on these expected within-subject effects for our treatment and control groups and the corresponding mean and standard deviations from our preliminary data, we estimate the between-group effect of the response to bupropion and response to escitalopram to have an ES Cohen's d = 0.97, which would require a total sample size of 36 (18 per group) for power >0.8 at alpha=0.05. Using 5000-fold resampling, with alpha = 0.05, sample power= 0.8, sample sizes of 18 per group (total sample size= 36) was large enough to estimate group differences. Figure 1 presents a graphical representation of the total sample sizes required for between-subject group comparisons of the FC response to bupropion versus escitalopram across the full range of power, demonstrating >80% power at the proposed total sample size of n=40. Hypothesis 2: For hypothesis 2a, the expect difference in motivation after bupropion versus escitalopram is based on the improvement in the EEfRT that has been previously established to be clinically and pharmacologically meaningful (≥10% change, 79, 80 representing a 0.10 increase in probability of hard choice choices) and standard deviations from our preliminary data for the EEfRT in MD patients. Thus, we expect a 0.10 ± 0.10 difference in mean probability of hard choices after bupropion compared to placebo and a medium to large ES (Cohen's d = 1.0), which will require a total sample size of 34 subjects (17 per group) for power >0.8 at alpha=0.05. For hypothesis 2b, our preliminary data on the relationship between VS-vmPFC FC and motivation, as measured by the EEfRT, demonstrated a correlation coefficient (r) of 0.43 (r² = 0.185). We expect a similar effect size for the relationship between change of FC and change in motivation and will need a sample size of 37 subjects to detect an overall relationship between change in FC and motivation with power >0.8 at alpha=0.05. Therefore, based on our sample size of n=40 (20 per group) we will have at least 80% power to detect significant differences for the proposed hypotheses to be tested under both Aims 1 and 2 at alpha=0.05.

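### The Aim 1 primary contrast uses baseline FC only by subtraction; pre-specifying regression adjustment for baseline FC is an optional precision gain, not the correction of an error

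*Combined protocol and SAP*

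**What the plan says.** Section 10, Aim 1, defines "Primary Endpoint: Targeted VS-vmPFC FC at 8 weeks". The fixed effects are given as "Predictors: group (bupropion vs escitalopram), time (baseline, 8 weeks), and group x time interactions", and the random part as "each subject's baseline (identity) as random effects". The covariate list opens with "Covariates: Primary: Age, sex, BMI, race". The additional covariates are illness-history items and "weeks on targeted dose of medication". Baseline FC appears in neither list.

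The targeted-FC paragraph in section 5 derives change from baseline, and section 11 powers the comparison on SDs of change: 0.16 after L-DOPA (standing in for bupropion) and 0.10 after placebo (standing in for escitalopram). The Aim 2 plan says that variation in baseline scores will be controlled for. Aim 1 has no such statement.

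**The concern.** The endpoint is FC at week 8 and the baseline scan is already collected, yet the model subtracts baseline FC instead of regressing on it. Subtraction fixes the slope on baseline at 1. When the correlation between visits is low or moderate, the best slope is below 1, and the change contrast carries baseline noise that adjustment would remove.

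What is at stake is precision in a 40-patient pilot. The planned effect, d = 0.97, comes from seven patients given L-DOPA and placebo, not the trial drugs, and the interim rule lets the trial continue at d between 0.3 and 0.6. At d = 0.6 with 20 per arm the change contrast has power of about 0.46. Baseline adjustment would give about 0.62, 0.56, 0.51 and 0.46 at correlations of 0.3, 0.5, 0.7 and 0.9, assuming equal SDs.

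**Working it through.** **Inputs from the documents.** Mean change 0.20 (SD 0.16) and 0.07 (SD 0.10); 20 analysed per arm; alpha 0.05 (two-sided assumed). **Inputs assumed.** The correlation ρ between baseline and week-8 FC, and k = week-8 SD / baseline SD.

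**1. The plan's own figure.** d = (0.20 − 0.07) / √((0.16² + 0.10²)/2) = 0.13 / 0.1334 = 0.974. With the noncentral t at d = 0.97, power is 0.783 at 17 per arm, 0.807 at 18 and 0.848 at 20. The stated 18 per group is reproduced.

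**2. What the planned contrast is.** With two visits, complete data, a subject random intercept and time-fixed covariates as main effects, the group-by-time estimate equals the difference in mean change. Random-intercept models fitted to simulated data gave the same value both ways (for example 0.5455 and 0.5455, with matching standard errors of 0.2331). Time-fixed covariates cancel from this term.

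**3. Variance of the adjusted contrast relative to the change contrast.** Ratio = k²(1 − ρ²) / (1 + k² − 2ρk), times 1 + 1/36 for estimating the slope with N = 40. With k = 1 this reduces to (1 + ρ)/2 × 37/36:
- ρ = 0.3: 0.65 × 1.0278 = 0.668 (33% lower)
- ρ = 0.5: 0.75 × 1.0278 = 0.771 (23% lower)
- ρ = 0.7: 0.85 × 1.0278 = 0.874 (13% lower; simulation 12%)
- ρ = 0.9: 0.95 × 1.0278 = 0.976 (2% lower; simulations 2-3%)

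At d = 0.97 the corresponding power is 0.955, 0.925, 0.892 and 0.856, against 0.848 for the change contrast.

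**4. Other assumptions.** Simulated ratios, 20 complete per arm, adjusting for baseline only:

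| Assumption | ρ 0.3 | 0.5 | 0.7 | 0.9 |
|---|---|---|---|---|
| k = 1 | 0.661 | 0.775 | 0.877 | 0.977 |
| k = 1.2 | 0.782 | 0.897 | 0.994 | 1.004 |
| k = 0.8 | 0.515 | 0.584 | 0.637 | 0.628 |
| Change SDs 0.16 and 0.10, through a larger week-8 SD on bupropion | 0.902 | 0.978 | 1.027 | 0.992 |

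For the last row, escitalopram has k = 1, and the bupropion k solves 1 + k² − 2ρk = (0.16/0.10)² × 2(1 − ρ), giving 1.94, 1.85, 1.71 and 1.47. The largest loss is about 3%. Adding sex, which stratification keeps nearly balanced, leaves these ratios essentially unchanged.

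**5. Adding age, BMI and race.** In the planned model these cancel from group-by-time. In a week-8 regression they do not. If unrelated to FC they add about 9-10% to the variance. At k = 1 the ratios become about 0.73, 0.84, 0.97 and 1.07. In the last scenario of the table they become about 0.98, 1.08, 1.13 and 1.08, with a worst case of 1.13 to 1.15 across simulations. Power at d = 0.97 can then fall from 0.85 to about 0.81.

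**The case against.** The strongest defence is that Aim 1 is internally consistent. The outcome is change, the model tests change, and the power calculation uses SDs of change and meets its target. Baseline FC is used, by subtraction. All of that stands.

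The random-effects phrase, "each subject's baseline (identity) as random effects", might be offered as baseline adjustment. It is ambiguous, but a random subject effect is not a regression on baseline FC. If adjustment was intended, the wording needs correcting anyway.

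It is also true that the documents cannot show that any gain exists, because neither ρ nor the visit SDs are given. If the tested contrast were the raw week-8 difference, which the plan does not exclude by name, the pattern in ρ would reverse (equal SDs): a loss of about 3% at ρ = 0, rising to a gain of about 48% at ρ = 0.7.

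Three stronger readings are tempting and unsupported:
- A reader might infer that the primary analysis is biased or underpowered. Under randomisation, complete data and time-fixed covariates it is neither. Using "weeks on targeted dose of medication", which arises after randomisation, or the step "The MMRM will also be augmented using Elastic net generalized regression models" would remove that assurance, but that is a separate issue.
- A reader might quote one headline range, such as a 3% loss to a 44% gain. Those ends come from different settings: the 3% from complete data with unequal SDs, the 44% from k = 0.8 and ρ = 0.3 with five baseline-only leavers per arm. They are not bounds.
- A reader might infer that every listed primary covariate should be added at the same time. Step 5 of the working shows that this can turn the gain into a loss.

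**Conclusion.** The point holds as an optional improvement. The planned group-by-time test is the unadjusted difference in change, and a pre-specified baseline-adjusted week-8 comparison would probably be more precise if ρ is low or moderate. With equal SDs the variance falls by about a third at ρ = 0.3 and by almost nothing at 0.9. The gain is larger if the week-8 SD is smaller than the baseline SD, and smaller if it is larger. The downside, adjusting for baseline FC and sex only, is about 3%. Confidence is medium. The structure of the model can be read from the text under the random-intercept reading, but every size depends on assumed correlations and SDs.

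**What to change.** Amend Aim 1 in section 10 to state that the week-8 arm difference in FC is estimated in one of two ways: with baseline FC as a fixed covariate, or in a mixed model with a common baseline mean across arms. Include sex as the stratification factor. Name the small-sample degrees of freedom and the variance form in advance. In simulation with 20 per arm the pooled variance held type I error at 0.046-0.055 even with unequal variances, while HC3 was conservative (0.030-0.045). Keep the change contrast as a sensitivity analysis, and clarify the random-effects wording. Do not make age, BMI and race part of this change.

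The cost is a SAP amendment and, in the baseline-adjusted model, a slope for baseline FC and a term for sex, with no new data or visits. Because the interim analysis breaks the blind after 16 completers and estimates the FC effect, the amendment must state whether it was made before or after that look.
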